Baseline: Parents or caregivers who are deemed eligible schedule a virtual appointment with the study coordinator to obtain informed consent and complete the baseline assessments (Demographics & psychological measures). Specifically, all participants will be asked to complete the Experience of Caregiving Inventory (ECI; Szmukler), the Family Questionnaire of Expressed Emotion (Wiedemann et al., 2002), Brief COPE (Carver, 1997), UCLA Loneliness Scale (Russell, 1996), Multidimensional Scale of Perceived Social Support (For control and Alternative form for Altitudes condition; Zimet et al., 1990), Modified Psychosis Attitudes Survey (PAS; Kopelovich et al., 2022), PTSD Checklist for DSM-5 (PCL-5, Weathers et al., 2013), Post Traumatic Growth Inventory (PTGI, Tedeschi & Calhoun, 1996), General Health Questionnaire-12 (GHQ-12; Goldberg, 1972), Self-Compassion Scale – Short Form (SCS-SF; Raes et al., 2011), and Five Facet Mindfulness Scale (FFMQ; Bohlmeijer et al., 2011). Additionally, all participants will complete a brief survey on engagement with services within the CSC program and outside the program (e.g., individual therapy, family groups outside of CSC, etc.). Altitudes condition participants are then oriented to the Altitudes platform if part of the open trial enrollment.

Study Treatment: Participants in the Altitudes condition will be given access to the digital platform Altitudes for approximately 6 months. Weekly engagement is decided by the participant. Digital access is available daily and digital access to family peer worker and online therapists is made available during their engagement with the platform. Control participants will have not interaction with the platform but may engage in routine clinical

care for parents and caregivers at CSC clinics, such as multifamily group and treatment planning sessions

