Participants in the Altitudes condition (parents and caregivers) will be given access to the Altitudes platform (which is considered a "non-significant risk" medical device and is described below) from their date of enrollment up to 6 months. Altitudes will be monitored daily (one hour per day) by trained family peer support specialists, master's level clinicians, Drs. [name] and [name], and/or graduate students in the Department of Psychology and Neuroscience at UNC. To facilitate and monitor engagement, a protocol is in place that directs moderators to contact participants via text message and/or email if he/she/they have not logged onto the platform for two weeks at the beginning of the service, primarily to assess for and troubleshoot logging into Altitudes or navigating the site. If a participant remains inactive for an additional two weeks, moderators will contact participants by phone to check in about any issues and discuss participants' goals for engaging in Altitudes. From that point forward, participants will be encouraged to contact moderators as needed with questions or helpseeking. Moderators will check in with participants monthly throughout the study to ensure Altitudes is meeting their treatment needs and to tailor content to the carers' interests. Caregiver participants may opt out of receiving monthly check-ins. Licensed clinical psychologists, Drs. [name] and/or [name], will lead weekly supervision calls to ensure appropriate care and support of participants involved in this project, to discuss case conceptualization and suggestions for engaging individuals on the platform, as well as to monitor any potential safety concerns.

Overview of Altitudes. Altitudes is an online social media platform that integrates: 1) peer-to-peer online social networking; 2) tailored interactive psychoeducation and psychosocial interventions; and 3) expert moderation.

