In addition, users will be able to "switch off" their profile and hide all of their existing comments on the system should they become concerned about their privacy during their course of participation. The limits of the moderator to respond (e.g., in a timely manner to emergencies) will also be fully explained. In order to protect the privacy of users who discontinue using the system, any accounts that have not been activated for one month may be deactivated following a follow-up telephone call from a moderator. Specifically, our disengagement protocol states that a participant will receive an email/call/text message if they have not logged onto the platform for two weeks. If another two weeks pass, we will call this person to check in about any potential issues or concerns. As noted

above, the moderation team will check in with participants on a monthly basis to ensure they are able to navigate the site with ease and to answer any questions they might have about the platform and any of its components/capabilities. Participants can opt out of these regular check ins from moderators at any time. If participants do not comply with the guidelines for safe use of Altitudes (e.g., discriminatory comments towards other users; disclosing identifying details of the identified patient) they will be excluded from the system.

Clinical safety: Although highly unlikely for the parent or caregiver, it is possible that participants may post information indicative of a clinical risk in their loved one, although participants will be advised that the service cannot respond to emergencies. Nonetheless, clinical risk will be monitored through manual and automated procedures. Information related to clinical risk will be screened daily by moderators and/or research staff. This information can include: 1) posts made by participants, which disclose evidence of deterioration in mental state of the young person in the care of participants; 2) participants reports or complaints on posts made by other users; and 3) automatically detected and blocked words posted by participants in the system. Additionally, clinical and family peer moderators will analyze the 'Community' feed to ensure that misinformation and falsehoods are not being spread by users of the platform.

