Any detected increased risk will activate the Altitudes safety protocol which includes a number of potential actions. Initially, the moderator will conduct a risk assessment based upon available information, inform the research team, and advise the participant on appropriate action, such as emergency services when necessary. In addition, the system incorporates visible emergency guidelines and contact information (i.e., on every webpage). Telephone numbers and contact details will be provided on each page of the website.

An automated keyword system has also been built in Altitudes which will be activated each time a participant posts a contribution containing potentially offensive words. When these words are detected the contribution will be blocked and the participant will be sent an automated email explaining that the message has been blocked and if they are facing distress then they should contact the emergency contact number as soon possible or if they are not facing distress they may like to consider rephrasing their post. An automated email will also be sent to the Altitudes moderator containing the attempted post.

In addition, a message will be available on each page providing a mobile telephone number carried by a member of the research team for any emergencies that are related specifically to the use of the Altitudes' system (e.g., highly inappropriate use of the system). Further, each page includes an "In Case of Emergency" link that provides about way to contact emergency services (911), the UNC crisis line [contact]), and crisis services (http://crisissolutionsnc.orge/; [988]).

Withdrawal criteria. Temporary or permanent withdrawal from Altitudes will be triggered by repeated inappropriate use of the system. This can include either suspension of a users' Altitudes account or restrictions regarding participation and use of Altitudes (i.e., the user is able to access therapeutic content and support from moderators but cannot post comments or participate in existing threads within the social network).

Non-Significant Risk Documentation

The present study has been deemed of non-significant risk (NSR) to participants.

Potential Benefits of the Research to Subjects and Others

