If researchers complete inductions or introductions to the site via video conference, the video or audio from these interviews will not be saved or recorded. Audio from qualitative interviews will be stored on a secure, password-protected server.

Identifiable data will only be shared with the clinicians of participants in the study with the permission of the participants (obtained during informed consent). Clinicians will be contacted if issues arise related to safety during the trial. As part of the informed consent process, all participants will be asked to provide the name and contact info of an emergency contact that we may contact if we become concerned about their safety or the safety of their loved one (e.g., physical and/or mental health) during the trial. Any limitations to privacy and confidentiality, including any indication of neglect or abuse of a minor, elder, or other vulnerable group, will be explicitly discussed with all participants during the informed consent process. We will not be sharing any confidential information with anybody outside of these clinicians.

Identifiable data will be maintained for 5 years following study completion. At that point, hard copies of identifiable data including consent forms and contact information will be shredded. Electronic data will be de-identified upon entry, with the exception of the subjects' birth dates for the purposes of calculating their exact age.

Safety Management

Adverse Events

System and privacy protection will be monitored by the study staff. Online safety will be monitored by the clinical and family peer moderators with supervision from the senior researcher staff (Drs. [name] and [name]). The moderators will have the authority to respond to online reports (e.g., remove offending material from the system)

and automated emails.

Clinical safety will be monitored proactively by the moderators through daily monitoring of the activity on Altitudes (i.e., twice a day during the weekdays and once a week on weekend days). In addition, information related to the well-being of participants could be brought to the attention of the research team from two potential sources: a) the online moderators via daily monitoring of the site; and b) the research coordinator at an interview.

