The research team will respond according to a *risk management algorithm*, which outlines the required response to potential indicators of clinical risk in terms of the source of the information. If the online moderator becomes aware of potential indicators of risk in the online application they will conduct an initial risk assessment, make the appropriate clinical response and inform the supervisor. If the study research coordinator becomes aware of an indicator of clinical risk they will inform their supervisor who will again respond clinically. The principal investigator will assess the criteria for withdrawal and potential suspension of usage restriction to a user's Altitudes account. The principal investigator will have ultimate responsibility for withdrawing participants from the study or restricting their Altitudes account.

Reporting of adverse events

Any adverse outcomes for participants, such as exposure to potentially harmful interactions through social networking, will be reported to University of North Carolina at Chapel Hill's (UNC-CH) Institutional Review Board (IRB). If a participant informs the moderators of an adverse event relating to the young person in their care or of any signs of deterioration in their mental health, the Altitudes moderators will communicate with the relevant clinicians where indicated.

RECRUITMENT STRATEGY

For recruitment, research staff have partnered with CSC clinics in previous studies and consultation. For this reason, research staff have extensive knowledge regarding recruiting from this target population. Research staff will inform the CSC providers and PSS about the study and its eligibility criteria to allow the treatment team the ability to identify potentially eligible participants. The treatment team will then approach potential parent and caregiver participants to gauge their interest in participating on the digital platform. If the person expresses interest or would like to know more about the study, the provider or PSS will pass along their information to research staff via referral forms to contact them to further discuss specifics about the study (e.g., describe the social networking and educational aspects of the platform). If the individual is still interested in participating, the client will be screened for eligibility. Upon meeting eligibility criteria, the individual will be scheduled for a baseline visit.

CONSENT PROCESS

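### The safety section explains daily monitoring by a schedule that, read literally, checks the platform on only one of the two weekend days; this is probably a one-word slip

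*Combined protocol and SAP*

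**What the plan says.** The combined protocol and SAP describes how often the platform is checked in three sections.

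- **Safety Management, Adverse Events.** Clinical safety is to be followed through daily monitoring of platform activity. A parenthesis introduced by *i.e.* gives the schedule: "twice a day during the weekdays and once a week on weekend days". The next sentence names, as one source of information on participants' well-being, "the online moderators via daily monitoring of the site".
- **Research Design & Methods, Overview.** "Altitudes will be monitored daily (one hour per day"), with the staff groups who do it listed after.
- **Altitudes safety protocol, Clinical safety.** "Information related to clinical risk will be screened daily by moderators and/or research staff".

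Three further statements give the context. The synopsis, under Study Treatment, says "Digital access is available daily". The Clinical safety text lists among the items to be screened "posts made by participants, which disclose evidence of deterioration in mental state of the young person in the care of participants". The risk management algorithm says: "If the online moderator becomes aware of potential indicators of risk in the online application they will conduct an initial risk assessment".

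**The concern.** The parenthesis is meant to define daily monitoring, but its weekend half does not describe it. One check per week, placed on weekend days, leaves either Saturday or Sunday without a scheduled look at the site. The weekday half, two checks a day, conflicts with nothing.

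This matters because it is the only place in the document that separates weekdays from weekends. Anyone who wants to know what weekend cover was promised will look here. Users can post on any day, and the moderator's part of the risk algorithm starts only when a moderator notices something. The keyword filter is described as reacting to potentially offensive words, so a plainly worded post about a young person getting worse may depend on a human check or on another user's report.

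Evaluating the safety and privacy protocol is also a listed study objective (synopsis, Study Objective(s); Assessment of Data). That evaluation needs one clear standard for how many checks were due.

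**Working it through.** The plan states no weekly total, so there is no figure of its own to reproduce. The check is a comparison of texts and a count.

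**Inputs**
- Weekdays per week: 5. Weekend days per week: 2.
- Weekday frequency: 2 checks a day (Adverse Events parenthesis).
- Weekend frequency: the disputed term in the same parenthesis.
- Standard to meet: daily, that is 7 of 7 days (Adverse Events, Overview, Clinical safety).

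**Formulas**
- Checks per week = 5 × 2 + weekend checks.
- Days covered = 5 + weekend days with at least one check.

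**Results**

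| Reading | Checks per week | Days covered | Daily? |
|---|---|---|---|
| Literal: one check per week, on a weekend day | 5 × 2 + 1 = 11 | 5 + 1 = 6 of 7 | No |
| Strained: each weekend day checked once in its week | 5 × 2 + 2 × 1 = 12 | 5 + 2 = 7 of 7 | Yes |
| Corrected: once a day on weekend days | 5 × 2 + 2 × 1 = 12 | 5 + 2 = 7 of 7 | Yes |

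Difference between the literal and corrected schedules: 12 − 11 = 1 scheduled manual check a week.

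**Comparison of texts.** Apart from the disputed phrase, four statements say daily: the term being explained in the same sentence, the sentence that follows, the Overview, and the Clinical safety paragraph. Nothing in the document supports a lighter weekend schedule. The literal reading contradicts all four. The strained reading and the corrected wording contradict none.

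**The case against.** The strongest reply is that this is proofreading. The commitment is to daily monitoring, the faulty words are a parenthetical explanation, and the intended meaning can be recovered from the rest of the document. The Clinical safety paragraph requires daily screening independently, so staff who follow the whole protocol would check on both weekend days. No document says that the rota is taken from the parenthesis. Three of the four supporting statements lie outside the faulty sentence, which makes the intended meaning fairly plain.

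Other protections would also continue on an unchecked day:
- Users can report posts to the moderator at any time (Online safety).
- Posts caught by the keyword filter are blocked, the user is emailed, and "An automated email will also be sent to the Altitudes moderator containing the attempted post".
- A research-team mobile number and emergency links appear on every page.
- Participants are told that the service cannot respond to emergencies.
- Risk may also come to light through the research coordinator at an interview.

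The protocol itself regards clinical risk in the caregivers as highly unlikely, and the young people are in, or have recently left, specialty care.

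All of this is fair, and it limits the weight of the point. It does not make the wording right. A safety schedule that agrees with its own headline only on a strained reading still needs correcting. The Altitudes Moderation Checklist (Expert Moderation) does not settle the matter: as described, it governs what is done in a session, and nothing shown says that it sets how often sessions happen at weekends.

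**Conclusion.** The concern holds, as a minor internal inconsistency in a safety procedure. On the literal reading the schedule falls one manual check and one day a week short of the daily monitoring promised elsewhere: 11 checks on 6 days against 12 checks on 7 days.

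This rests on two assumptions. The first is that the phrase is read as one weekend check per week, which is its natural sense though not the only possible one. The second, needed for any practical effect, is that staff follow the parenthesis rather than the other daily statements. The document does not show that they would, and the effect may never occur. That once a day was intended is an inference: it is the smallest edit that brings every statement into agreement, but the text does not prove it.

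No claim is made about the length of any gap in hours or the chance of a missed event. No outcome, estimate, analysis or sample size is affected.

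**What to change.** In Safety Management, Adverse Events, change *week* to *day* in the weekend half of the parenthesis, so that each weekend day is checked once a day. The schedule then gives 12 checks on 7 of 7 days and matches the Overview, the Clinical safety paragraph and the adjoining sentence. No other text needs to change.

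The cost is one word. It adds no work beyond the daily monitoring already promised. The Protocol Amendments section requires modifications to be notified to the IRB, so the correction can go in with the next amendment.
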